### 5.3 Secondary endpoints

#### 5.3.1 Rate of freedom from catheter-related bloodstream infection (CRBSI) defined by 2019 KDOQI Guidelines for CRBSI.

##### Binary Analysis

Subject will be considered as having CRBSI for a given visit if the subject has experienced device-related bloodstream infection prior to the upper limit of visit window for the visit:

- **AE CRF Page:** AE start date  $\leq$  upper limit of the visit window AND Relationship to study Device: Equals 'Related' or 'Likely Related' AND Was event infectious: Equals Yes AND Select Type of Infection: Equals Blood Stream and Were there clinical manifestation and at least 1 positive blood culture with no apparent source: Equals Yes; subject will be considered as a failure at the AE date

If the subject has not become failure and experience one of the following events prior to the lower limit of visit window, then subject will be considered as non-evaluable at the earliest occurrence of following event dates.

- Catheter has been removed due to Kidney Transplant, Transferred to AVG/AVF, Peritoneal Dialysis, Withdrawal of Care, or Other reasons

***Hemodialysis Catheter Re-Interventions CRF page:*** Catheter removal Equals Yes AND Reason for

*catheter removal Equals: Kidney Transplant, Transferred to AVG/AVF, Peritoneal Dialysis, Withdrawal of Care, or Other*

OR

- Subject has discontinued from the study.

Else subject will be considered as a success (freedom from CRBSI) for a given visit.

The rate of freedom from CRBSI will be reported with 95% confidence interval from the exact binomial method. The analysis will be performed on the mITT population through 1-month, 3-months, 6-months, and 12-months.

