3.2 Secondary Endpoints

The following secondary endpoints will be evaluated using descriptive statistics to provide further information related to the safety and performance of the Pristine™ Long-Term Hemodialysis Catheter. All secondary endpoints will be summarized with descriptive statistics.

- *Rate of freedom from catheter-related bloodstream infection (CRBSI)*, defined by 2019 KDOQI Guidelines for CRBSI through 1-month, 3-months, 6-months, and 12 months post-index procedure.

- *Rate of freedom from Device and/or Procedure-related adverse events*, at 1-month, 3-months, 6-months, and 12 months post-index procedure.
- *Rate of Technical Success*, defined as the successful placement of the Pristine™ Long-Term Hemodialysis Catheter, as assessed by the Investigator during the Index Procedure.
- *Overall Participant Survival Rate* at 1-month, 3-months, 6-months, and 12 months post-index procedure, defined as the proportion of participants that have not died from any catheter related complication.
- *Overall Catheter Survival Rate* at 1-month, 3-months, 6-months, and 12 months post-index procedure, defined as the proportion of Pristine™ Catheters that have not been removed for any cause.
- *Overall Patency Rate*, at 1-month, 3-month, 6-months, and 12-months post-index procedure, defined as the Pristine™ catheter having the ability to achieve a mean dialysis blood flow of $\geq 300\text{mL/min}$ without need for additional interventions.^{5,6}

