Device Deficiency	Any inadequacy of a medical device with respects to its identity, quality, durability, reliability, usability, safety, or performance. Device deficiencies include malfunctions, use errors, and inadequacy in the information supplied by the manufacturer including labeling. A device malfunction is defined as a failure of a medical device to perform in accordance with its intended purpose when used in accordance with the IFU or CIP. Device deficiencies are only applicable to the Pristine™ Catheter.
End Stage Renal Disease (ESRD)	Last stage of Chronic Kidney Disease. When the kidneys stop working well enough to meet the needs of daily life.
Enrolled Participant	A participant who has signed the ICF for this investigation.
Independent	Not involved in the development of the investigation device or the conduct of a clinical investigation, except for their specifically assigned responsibilities, in order to avoid bias or a conflict of interest.
Index Procedure	The initial procedure intended to place the Pristine™ Catheter for dialysis access.
Informed Consent	Process by which an individual voluntarily confirms willingness to participate in a particular clinical investigation, after having been informed of all aspects of the investigation that are relevant for the decision to participate.
Investigational Site	Institution or site where the clinical investigation is carried out.
KDOQI VA-2019 CVC-related infection definition	“Clinical manifestations and at least 1 positive BC from a peripheral source (dialysis circuit or vein) and no other apparent source, with either positive semiquantitative (>15 CFU/ catheter segment, hub or tip) or quantitative (>102 CFU/catheter segment, eg, hub or tip) culture, whereby the same organism (species and antibiogram) is isolated from the catheter segment (eg, hub or tip) and a peripheral source (dialysis circuit or vein) blood sample. If available, the following would be supportive: Simultaneous quantitative cultures

Term	Definition
	of blood samples with a ratio of $\geq 3:1$ (catheter hub/tip vs peripheral [dialysis circuit/vein]); differential period of catheter culture versus peripheral BC positivity of 2 hours.”

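### The SAP's CRBSI event rule does not implement the KDOQI 2019 definition that the endpoint is labelled with: it drops the matching catheter culture and adds a device-relatedness condition

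*SAP*

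**What the plan says.** Protocol 3.2 lists freedom from CRBSI as a secondary endpoint, "defined by 2019 KDOQI Guidelines for CRBSI through 1-month, 3-months, 6-months, and 12 months post-index procedure". The heading of SAP 5.3.1 repeats the label: "Rate of freedom from catheter-related bloodstream infection (CRBSI) defined by 2019 KDOQI Guidelines for CRBSI".

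Protocol Appendix A gives the only KDOQI infection definition in either document. Its entry is titled as a CVC-related infection definition. It starts with "Clinical manifestations and at least 1 positive BC from a peripheral source (dialysis circuit or vein) and no other apparent source", continues "with either positive semiquantitative (>15 CFU/ catheter segment, hub or tip) or quantitative" culture, and adds "whereby the same organism (species and antibiogram) is isolated from the catheter segment (eg, hub or tip) and a peripheral source". Only the simultaneous culture ratio and the differential time to positivity are described as supportive if available.

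The Binary Analysis in SAP 5.3.1 counts an event when all of these hold on the AE CRF page: the start date is within the visit window; the relationship to the device is Related or Likely Related; the event is infectious; its type is bloodstream; and the answer is Yes to "Were there clinical manifestation and at least 1 positive blood culture with no apparent source". The Kaplan-Meier analysis gives no other definition of the event.

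Protocol 10.6 makes the secondary endpoints descriptive, without hypothesis tests. Protocol 7.1.5 requires no laboratory tests. Protocol 3 and SAP 1.2 say that the study's results are intended for the device's labeling.

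**The concern.** A rate carrying a guideline's name is read as a count under that guideline's definition. Here the rule that produces the rate differs from the definition in two ways, and neither document explains either one.

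The study justifies its design in Protocol 4.2 partly by the need for consistent definitions across tunneled-catheter studies. CRBSI is its only infection-specific secondary endpoint. If the rate reaches the labeling or a publication as KDOQI-defined, a reader would compare it with rates built on a different event and could not tell in which direction the comparison is off.

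**Working it through.** **Step 1. Set the two definitions side by side.**

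| Element | Protocol Appendix A | SAP 5.3.1 rule | Effect on the event |
|---|---|---|---|
| Clinical manifestations | Required | Required | None |
| Positive blood culture | At least one, from a peripheral source | At least one, source not specified | Broader |
| Other source excluded | No *other* apparent source | No apparent source | Ambiguous |
| Positive catheter segment, hub or tip culture | Required | Absent | Broader |
| Same organism in catheter and blood | Required | Absent | Broader |
| Device relationship Related or Likely Related | Absent | Required | Narrower |

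The third row is a wording matter with a possible consequence. Read literally, an infection whose apparent source is the catheter itself does not have *no apparent source*, so the item could be answered No for the very event that it is meant to capture.

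**Step 2. See what the relatedness condition excludes.** Protocol 9.3 restricts device-related to events directly attributable to the device and makes procedure-related a separate category. SAP 5.3.2 counts events related to the device *or* the procedure; SAP 5.3.1 counts device-related events only. A culture-positive bloodstream infection attributed only to the insertion procedure is therefore a failure under 5.3.2. Under 5.3.1, if the participant is still evaluable at that visit, it counts as freedom from CRBSI.

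**Step 3. Ask how far the two counts could differ.** The documents give no expected CRBSI rate, so there is no plan figure to reproduce. The inputs below are assumptions, apart from the sample size of 142 (SAP 2.4), and all 142 are taken as evaluable.

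- B = participants with clinical signs, a positive blood culture and no other source: 8 or 14.
- r = share of B judged device-related: 50% to 100%.
- c = share of B with a matching catheter culture: 40% to 100%.
- SAP events = B × r and KDOQI events = B × c, each rounded to a whole number.
- Difference in freedom rate, SAP minus KDOQI = (KDOQI events − SAP events) / 142.

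| B | r | c | SAP events: % free (exact 95% CI) | KDOQI events: % free (exact 95% CI) | Difference, points |
|---|---|---|---|---|---|
| 14 | 100% | 40% | 14: 90.1 (84.0–94.5) | 6: 95.8 (91.0–98.4) | (6 − 14)/142 = −5.6 |
| 14 | 50% | 100% | 7: 95.1 (90.1–98.0) | 14: 90.1 (84.0–94.5) | (14 − 7)/142 = +4.9 |
| 8 | 100% | 40% | 8: 94.4 (89.2–97.5) | 3: 97.9 (94.0–99.6) | (3 − 8)/142 = −3.5 |
| 8 | 50% | 100% | 4: 97.2 (92.9–99.2) | 8: 94.4 (89.2–97.5) | (8 − 4)/142 = +2.8 |

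With r = 80% and c = 70%, B = 8 gives 6 events under both rules and no difference. The sign depends on r and c, and the documents give neither.

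**The case against.** The strongest case on the other side is that this is a labelling inconsistency in one of six descriptive secondary endpoints. There is no alpha, power or target rate for CRBSI, and no comparison with KDOQI-based rates is planned. The tested infection outcome is the infectious component of the primary endpoint. All of this stands, and it limits the weight of the point. It does not make the label correct.

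A reader might infer that the relatedness condition lets an unblinded investigator remove culture-positive infections at will. The documents do not support that. Under Table 3 of Protocol 9.3, Not Related needs a documented alternative etiology, which conflicts with answering Yes to the no-source item. Unlikely Related needs both an improbable temporal relationship and a plausible explanation in underlying disease. Some discretion remains, and there is no blinding (SAP 2.3) and no endpoint adjudication described (Protocol 9.5 has only a Medical Monitor). That the site investigator makes the call is itself an inference. Excluded events would still appear in the AE tables and listings of SAP 7.

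A reader might also infer that the rule flatters the device. Take the filter alone and assume that 10% have a qualifying infection and 10% to 30% of those are judged Unlikely Related. Freedom then reads 1 − 0.10 × 0.9 = 91% to 1 − 0.10 × 0.7 = 93%, against 90%. But that 90% is the rate without the filter, not the KDOQI rate, and the missing catheter culture pushes the other way.

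Dropping the relatedness condition altogether would leave attribution to the catheter resting only on exclusion of other sources. That is fair, and it is why both counts should be shown. Finally, the CRF and SAP Appendix 2 are not available here and may hold more detail, but the SAP 5.3.1 rule does not refer to them.

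**Conclusion.** The inconsistency is real and follows from the text alone: SAP 5.3.1, applied as written, gives a rate that is not CRBSI as Appendix A defines it. The rule is broader in its microbiology and narrower in its attribution.

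The size and sign of the net effect cannot be derived. The range of −5.6 to +4.9 points rests wholly on the assumed counts and shares in the working, so it illustrates scale and is not an estimate. No claim of bias in the device's favour is supported. Nor do the documents make CRBSI the main infection claim: the labeling statement is general and names no CRBSI claim. Type I error, power and the primary test are untouched.

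The point is worth correcting before analysis because the correction is cheap and a reader of the reported rate could not make it afterwards. It assumes that the Appendix A entry, the only KDOQI text present, is the definition meant in Protocol 3.2.

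**What to change.** In SAP 5.3.1:

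1. Stop describing the count as KDOQI-defined. Name it for what it is: device-related bloodstream infection with clinical manifestations, one or more positive blood cultures and no other apparent source. State that this departs from the definition cited in Protocol 3.2.
2. Correct the source wording to no *other* apparent source, in line with Appendix A.
3. Report beside it the same count without the device-relatedness condition, from the AE CRF fields that the rule already uses.
4. Use the KDOQI label only for events shown to meet the full Appendix A definition, where catheter culture results from standard care are available. Give the number of events with no catheter culture, so that untested cases are not read as KDOQI-negative.

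The cost is one or two extra table rows, a possibly less favourable rate in the unfiltered row, and some source review if the KDOQI subset is reported, since the rule shows no field for catheter culture or organism match. No additional cultures are needed.

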### **Kaplan-Meier (KM) Analysis**

KM analysis will be used to estimate the time from the date of index procedure to the first CRBSI event and to determine the rate of freedom from CRBSI at 1-, 3-, 6-, and 12-months. CRBSI is considered as the event.

Subjects that have not reached CRBSI (event) will be censored or considered event free as described below.

- If the subject has experienced following events, subject will be censored at the earliest date of those events.
  - Catheter has been removed due to Kidney Transplant, Transferred to AVG/AVF, Peritoneal Dialysis, Withdrawal of Care, or Other reasons
  - Subject has discontinued from the study.

Note: How to assess the above events has been described in **Error! Reference source not found.** the Binary Analysis section.

- All the other subjects will be considered event free and will be censored on visit day (visit day can vary from lower limit to upper limit of visit window).

This endpoint will be evaluated on the mITT populations through 1-month, 3-months, 6-months, and 12-months.

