### 5.3.5 Overall Catheter Survival Rate at 1-month, 3-months, 6-months, and 12-months post-index procedure, defined as the proportion of Pristine™ Catheters that have not been removed for any cause.

#### Binary Analysis

Subject will be considered as a failure of the endpoint for a given visit if the subject has the catheter removed due to infection or catheter dysfunction prior to the upper limit of visit window for the visit:

- **Hemodialysis Catheter Re-interventions CRF Page:** Date of Re-Intervention: <= upper limit of the visit window AND Reason for catheter removal: Equals Infection/Catheter Dysfunction); subject will be considered as a failure at the re-intervention date

If the subject has not become failure and experience one of the following events prior to the lower limit of visit window, then subject will be considered as non-evaluable at the earliest occurrence of following event dates.

- Catheter has been removed due to Kidney Transplant, Transferred to AVG/AVF, Peritoneal Dialysis, Withdrawal of Care, or Other reasons
  - *Hemodialysis Catheter Re-Interventions CRF page: Catheter removal Equals Yes AND Reason for catheter removal Equals: Kidney Transplant, Transferred to AVG/AVF, Peritoneal Dialysis, Withdrawal of Care, or Other*

OR

- Subject has discontinued from the study.

If the subject has experienced any of the above **non-evaluable** events prior to the lower limit of visit window subject will be counted as a non-evaluable for a given visit. Else subject will be considered as a success of the endpoint for a given visit.

The overall catheter survival rate will be reported with 95% confidence interval from the exact binomial method. The analysis will be performed on the mITT population through 1-month, 3-months, 6-months, and 12-months.

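### The binary secondary rates in SAP 5.3 use a denominator selected on outcome, so the exact binomial interval is not valid for the risk at a visit; the planned Kaplan-Meier estimate should be the reported rate

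*SAP*

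**What the plan says.** SAP 5.3.1 (CRBSI) sets the pattern. A failure is an event "prior to the upper limit of visit window for the visit". If a subject has not failed and has one of two exits "prior to the lower limit of visit window, then subject will be considered as non-evaluable at the earliest occurrence". One exit is study discontinuation. The other is "Catheter has been removed due to Kidney Transplant, Transferred to AVG/AVF, Peritoneal Dialysis, Withdrawal of Care, or Other reasons". For everyone left, "Else subject will be considered as a success (freedom from CRBSI) for a given visit". The resulting rate "will be reported with 95% confidence interval from the exact binomial method".

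Sections 5.3.2, 5.3.4, 5.3.5 and 5.3.6 repeat the rule with their own events. For catheter survival in 5.3.5, "The overall catheter survival rate will be reported with 95% confidence interval from the exact binomial method".

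Each of these sections also plans a Kaplan-Meier analysis. In 5.3.1, "KM analysis will be used to estimate the time from the date of index procedure to the first CRBSI event", and "Subjects that have not reached CRBSI (event) will be censored or considered event free as described below"; the same leavers are censored there. SAP 5.3 does not say which of the two results is the endpoint's rate, and it names an interval method only for the binary one. Protocol 10.6 promises 95% intervals without a method and makes the secondary endpoints descriptive, with no tests.

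**The concern.** Whether a subject is in the denominator depends on the outcome. Someone who fails early is kept whatever would have happened later. Someone who is event-free until transfer to a fistula, transplant or discontinuation is deleted. Exact binomial limits assume a fixed set of subjects with a common risk, and they cannot repair a denominator chosen this way.

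Exits should be common here. Protocol 2.1 describes these catheters as a bridge to a matured fistula or a donor organ, Protocol 7.5 ends participation at catheter removal, and Protocol 8.1 stops data collection at discontinuation. Each endpoint will therefore have two rates per visit, and the gap between them will tend to widen with follow-up. Protocol section 3 intends the study's information for the device labeling, so the rate to be quoted should be fixed beforehand.

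**Working it through.** **Inputs from the documents.** Windows (SAP 2.6, Table 1), taking months as 90, 180 and 365 days: lower/upper limits L/U of 75/105, 165/195 and 335/395. Attrition is 15% through 90 days (SAP 2.4), the only exit figure given. The plan states no event rate, removal rate or precision for the secondary endpoints, so there is no secondary figure to reproduce. The 15% does appear to be built into the primary sample size: about 10,850 days give 80% power with an exact Poisson test, and 10,850/0.85 = 12,765.

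**Assumptions.** Constant hazards; exits independent of the event; 142 mITT subjects; all exits by the listed removal reasons or discontinuation; the 15% continuing at the same rate, so exit by day 365 is 1 − 0.85^(365/90) = 48%; event risks of 5% to 30%. True risk means the net risk R at the nominal day T.

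**Formulas.** h = −ln(1 − R)/T; c = −ln(0.85)/90 = 0.001806; s = h + c.
- Counted failures: F = (h/s)(1 − e^(−sU))
- Deleted leavers: D = (c/s)(1 − e^(−sL))
- Expected binary failure rate: q = F/(1 − D)

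**12 months, R = 20%.** h = 0.000611 and s = 0.002417. F = 0.1556, D = 0.4146, q = 0.1556/0.5854 = 26.6%. Setting L = U = 365 gives 26.3% at 48% exit, so deleting leavers, not the window, drives the excess.

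Coverage of the nominal 95% interval for R is from 2,000 simulated trials per row; direct summation over the binomial agrees within 2 points.

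| True 12-month risk | F | D | q | Coverage |
|---|---|---|---|---|
| 5% | 0.0387 | 0.4444 | 7.0% | 90% |
| 10% | 0.0776 | 0.4347 | 13.7% | 83% |
| 20% | 0.1556 | 0.4146 | 26.6% | 72% |
| 30% | 0.2342 | 0.3934 | 38.6% | 62% |

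Varying the assumed 12-month exit to 30%, 50% and 70%: a true 20% becomes 24.0%, 26.9% and 32.0%; a true 10% becomes 12.2%, 13.9% and 17.1%.

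**6 months, R = 20%.** Exit is 1 − 0.85² = 27.75%. F = 0.1823, D = 0.2342, q = 23.8%; with no window gap, 22.9%.

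**3 months, R = 20%.** h = 0.002479 and s = 0.004285. F = 0.2096, D = 0.1158, q = 23.7%. With L = U = 90, F = 0.1852, D = 0.1348 and q = 21.4%. The rest comes from counting to day 105, where the net risk is itself 1 − e^(−0.002479 × 105) = 22.9%. Against that day-105 risk, coverage is 95–96%.

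**Kaplan-Meier on the same simulated data.** Mean failure was 0.049–0.050, 0.099–0.101, 0.199–0.201 and 0.298–0.303 for true 5%, 10%, 20% and 30%, with coverage of 94–97%. This also assumes visits fall on or after the nominal day.

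**Where the direction changes.**
- *5.3.1 and 5.3.4.* Removal for infection or dysfunction is not a listed exit. Read literally, a subject with such a removal and no endpoint event is a success. At 12 months, true 20% and 48% exit, the binary rate is 22.6% (coverage 92%) if 20% have such removals and 18.8% (96%) if 40% do. If they are instead treated as discontinued, it is 28.6% (65%) at 20%.
- *5.3.5.* The stated definition is removal for any cause, but only infection or dysfunction removal is programmed as failure. With a 20% risk of that and 48% other exits, all taken to be removals, any-cause removal is 1 − 0.80 × 0.52 = 58.4%. The rule gives 26.5%.
- *5.3.6.* Any re-intervention after first dialysis is a failure, and removals are logged on the re-intervention form, so an elective removal may itself count as a failure.

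**The case against.** The strongest reply is that little depends on this. The endpoints carry no test, Kaplan-Meier is already planned for each of them, and the table shells (SAP Appendix 1.1 and 1.2), which may settle the headline rate, are listed but not available to read. At 3 months, when the primary analysis is reported, dropping leavers has little effect. For catheter-related death in 5.3.4 the absolute shift is also small: the feasibility study had 9 deaths, none attributed to device or procedure, and an assumed 1% risk with 48% exit becomes only 1.4%. All of this stands, and it limits the priority. It does not make the binary rate a sound estimate at 12 months, and the SAP text leaves both rates with equal standing.

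A reader might infer that all these rates are biased against the device and that their intervals generally miss the truth. The documents do not support that. The direction depends on how infection and dysfunction removals are coded, and it reverses for 5.3.5 against its own definition. Under-coverage is graded: most intervals still cover in every row of the table, and severe failure needs both high event risk and high exit. Nor can the whole 3-month rise from 20% to 23.7% be put down to deleted leavers.

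**Conclusion.** The point holds in this limited form. The binary rule conditions the denominator on outcome, and its exact binomial interval is not valid for the risk at the visit. For listed removals and discontinuations it overstates failure: by about 4 points on a true 10% and 7 points on a true 20% at 12 months, and by 1.4 points on 20% at 3 months once the window extension is set aside.

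These sizes rest on assumed event risks, constant independent hazards and a constant extension of the 15% attrition. The structural fault does not depend on those values. The net direction for a given endpoint cannot be stated until the handling of other removals is settled. The primary endpoint and the sample size are unaffected.

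**What to change.** In SAP 5.3:
1. Name the Kaplan-Meier estimate as the reported rate at 1, 3, 6 and 12 months, with a stated 95% interval (for example Greenwood, log-log). Use cumulative incidence where death or removal is treated as competing, and say for which endpoints. The choice matters: in the 12-month, 20% case the crude cumulative incidence is 14.8%.
2. Keep the binary tables as counts of failures, event-free and non-evaluable subjects.
3. State how infection and dysfunction removals are handled in 5.3.1, 5.3.2 and 5.3.4, in both analyses; the Kaplan-Meier text has no censoring rule for them either. State also whether a removal counts as a re-intervention in 5.3.6.
4. Reconcile the 5.3.5 event with its any-cause definition before its Kaplan-Meier curve becomes the headline, because that curve uses the same narrow event.

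The cost is SAP wording and matching table shells, with no new data. The downside is that the simple proportion is no longer the headline figure.

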7.2.1 Clinical Procedure

After the PI, or authorized designee(s), has determined that the participant is eligible for participation based on the criteria listed in Section 5.1 and 5.2, the participant may be enrolled and undergo the Pristine™ Catheter placement procedure. Examinations, evaluations, procedural preparation, angiography, treatment, and hospital / facility discharge procedures will be conducted per the investigational site's SOC.

The placement of the Pristine™ Catheter, will be per the investigational site's SOC and must adhere to the device IFU. Operators of the Pristine™ Catheter must be approved by the Sponsor as an operator in writing before conducting an index procedure on enrolled participants (refer also to Section 13.3). For detailed information on device use and procedural medication recommendations, reference the IFU.

Enrolled participants will continue clinical participation through the 12-month follow-up period. Participants into whom the Pristine™ Catheter was not introduced should be treated per SOC and the reason documented on the appropriate eCRF. Participation for these participants will end at time of the index procedure.

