### **5.3.4 Overall Participant Survival Rate at 1-month, 3-months, 6-months, and 12-months post-index procedure, defined as the proportion of participants that have not died from any catheter related complication.**

## Binary Analysis

Subject will be considered as a failure of the endpoint for a given visit if the subject has experienced the death due to a catheter-related complication prior to the upper limit of visit window for the visit:

- **Disposition-End of Study CRF Page:** Date of Death <= upper limit of the visit window  
**AND AE CRF Page:** Relationship to Device: Is 'Related' or 'Likely Related' AND Does the Event Meet the Definition of an SAE: Is Yes AND Results in Death: Is Yes and subject will be considered as a failure at the Death date

If the subject has not become failure and experience one of the following events prior to the lower limit of visit window, then subject will be considered as non-evaluable at the earliest occurrence of following event dates.

- Catheter has been removed due to Kidney Transplant, Transferred to AVG/AVF, Peritoneal Dialysis, Withdrawal of Care, or Other reasons
  - *Hemodialysis Catheter Re-Interventions CRF page: Catheter removal Equals Yes AND Reason for catheter removal Equals: Kidney Transplant, Transferred to AVG/AVF, Peritoneal Dialysis, Withdrawal of Care, or Other*

OR

- Subject has discontinued from the study.

If the subject has experienced any of the above non-evaluable events prior to the lower limit of visit window subject will be counted as a non-evaluable for a given visit. Else subject will be considered as a success of the endpoint for a given visit.

The overall participant survival rate will be reported with 95% confidence interval from the exact binomial method. The analysis will be performed on the mITT population through 1-month, 3-months, 6-months, and 12-months.

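### SAP 5.3.1 neither counts nor censors catheter removal for infection or dysfunction, so Kaplan-Meier freedom from CRBSI is overstated if those participants stay in follow-up

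*SAP*

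**What the plan says.** SAP 5.3.1 defines failure from the adverse event form: "Subject will be considered as having CRBSI for a given visit if the subject has experienced device-related bloodstream infection prior to the upper limit" of the visit window. The event must be judged related or likely related to the device, be of bloodstream type, and have clinical signs with a positive blood culture.

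A participant who has not failed leaves the evaluable set (binary analysis) or is censored (KM analysis) by two routes only:

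- "Catheter has been removed due to Kidney Transplant, Transferred to AVG/AVF, Peritoneal Dialysis, Withdrawal of Care, or Other reasons"
- "Subject has discontinued from the study"

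The defaults for everyone else are "Else subject will be considered as a success (freedom from CRBSI) for a given visit" in the binary analysis and "All the other subjects will be considered event free and will be censored on visit day" in the KM analysis.

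Infection and dysfunction are separate answers on the removal-reason field. SAP 5.3.5 uses them as its failure event ("Reason for catheter removal: Equals Infection/Catheter Dysfunction") alongside the same short list of non-evaluable removals.

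On staying in the study, Protocol 7.2.1 says "Enrolled participants will continue clinical participation through the 12-month follow-up period". Protocol 7.5 keeps a participant with a placed catheter in the study until required follow-up is complete or until the day the catheter is removed, and reserves completion for those followed through 12 months.

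**The concern.** The short removal list fits SAP 5.3.5, where removal for infection or dysfunction is itself the event. In SAP 5.3.1 the same list leaves a gap: these removals are neither an event nor a reason to stop counting time. A participant whose catheter comes out because a fistula is ready is dropped, while one whose catheter comes out because it failed is scored free from CRBSI. The SAP gives no reason for the difference.

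Because a CRBSI must be attributed to the device, a participant has little risk of one once the catheter is out. Take a catheter removed for thrombosis on day 20. If the participant stays in follow-up, the remaining 365 − 20 = 345 days of a 12-month period count as event-free time with no study catheter. Early device failures would then raise the reported freedom from infection. Protocol section 3 intends the study's results for the device labeling, and Protocol 4.2 ranks infection rate among the most important values a catheter study reports.

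**Working it through.** **Does the gap operate?** It does only if a participant whose catheter is removed for infection or dysfunction is not recorded as discontinued.

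- Pointing to discontinuation: Protocol 7.5 ends participation on the day of removal.
- Pointing the other way: Protocol 7.2.1 continues participation to 12 months. Appendix A lists withdrawn consent, withdrawal by the investigator, loss to follow-up and death as causes of premature discontinuation, and omits removal. Protocol 7.4.1 makes the flow data conditional on dialysis through the study catheter, so it foresees visits without it. SAP 5.2.1 and 5.3.1 list removal and discontinuation as separate triggers.

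The documents do not settle this. A participant who leaves at removal, is not coded as discontinued and has no later visit also has no defined KM visit day.

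**How large is the effect?** The documents give no CRBSI or removal rate, so there is no figure to reproduce and every input below is an assumption. Let h be the daily CRBSI hazard, f the 12-month probability of removal for infection or dysfunction without CRBSI, and r = −ln(1 − f)/365. Hazards are constant and independent, and there is no CRBSI risk after removal. With no listed removals or discontinuations:

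- KM censored at removal = exp(−365h)
- KM with removals kept at risk = 1 − [h/(h + r)] × [1 − exp(−365(h + r))]

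Example: h = 0.001 and f = 20% give r = 0.000611. Censored: exp(−0.365) = 69.4%. Kept: 1 − 0.6206 × (1 − 0.5554) = 72.4%.

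| CRBSI per 1000 days | f | Censored | Kept | Excess |
|---|---|---|---|---|
| 1.0 | 20% | 69.4% | 72.4% | 3.0 |
| 1.0 | 40% | 69.4% | 75.7% | 6.3 |
| 0.5 | 20% | 83.3% | 85.0% | 1.7 |
| 0.5 | 40% | 83.3% | 86.8% | 3.5 |

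A second set of assumptions used lower 12-month CRBSI risks (5% to 20%), f from 10% to 30%, and either none or 40% of participants with a listed removal or discontinuation:

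| 12-month CRBSI risk | Censored | Kept |
|---|---|---|
| 5% | 95.0% | 95.3 to 95.9% |
| 10% | 90.0% | 90.5 to 91.8% |
| 20% | 80.0% | 81.0 to 83.5% |

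The excess is about 0.3 to 3.5 points at 12 months and at most about 0.3 at 3 months (94.9% against 94.6%). About 10% to 39% of the 12-month binary successes in these scenarios have no study catheter.

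**The binary rate.** Let A be the proportion still event free with the catheter in place at 12 months, F the proportion with CRBSI and R the proportion removed for infection or dysfunction. The SAP rule gives (A + R)/(A + R + F). Making these removals non-evaluable gives A/(A + F).

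- h = 0.001, f = 20%, no listed removals: A = 0.555 and F = 0.276. The SAP rule gives 72.4%. The non-evaluable rule gives 0.555/0.831 = 66.8%. Against 69.4% the errors are +3.0 and −2.6 points.
- h = 0.001, f = 40%: 75.7% and 63.1%, errors of +6.3 and −6.3 points.
- h = 0.001, f = 20%, with 40% listed removals or discontinuations: A = 0.333, R = 0.135 and F = 0.221. The SAP rule gives 0.469/0.690 = 67.9%, below 69.4%.

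**The case against.** The strongest reply is Protocol 7.5. It addresses removal directly, whereas 7.2.1 is a general statement. If sites code exit at removal as discontinuation, the SAP's second route already censors these participants and the excess is zero. The SAP's derived data specification (its Appendix 2), known here only by title, may settle this. The reply stands to this extent: it makes the effect conditional, but it does not close the gap, because Appendix A and Protocol 7.4.1 point the other way.

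The list may also be deliberate. It resembles the access censoring events in Protocol Appendix A. Keeping removed participants at risk also moves toward one minus the cumulative incidence of CRBSI with removal as a competing event, which is a legitimate quantity. But the SAP does not name that quantity, and censoring the other removals does not fit it.

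Two further points stand. The endpoint is one of six descriptive secondaries (Protocol 3.2 and 10.6), so no type I error or power is affected. Infectious complications also enter the primary endpoint, and early failures are reported in SAP 5.3.5 and 5.3.6, so this is not the only place where they show.

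A reader might infer that the bias is always upward. That fails for the binary rate: dropping other removals while keeping failures can pull it below the catheter-in-place value. A reader might also infer that time after removal carries no risk at all. The SAP's event rule does not require the catheter to be in place, so a related bloodstream infection soon after removal still counts.

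**Conclusion.** The gap in SAP 5.3.1 is real, and its effect is conditional. If removal for infection or dysfunction is not coded as discontinuation, KM freedom from CRBSI with the catheter in place is overstated. The excess is roughly 0.3 to 3.5 points at 12 months and at most about 0.3 at 3 months in the main assumed scenarios, and about 6 points at 12 months at 1.0 CRBSI per 1000 days with 40% failure removals. If it is coded as discontinuation, there is no excess. These sizes rest on assumed constant, independent hazards.

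The documents do not support the flat statement that these participants are scored as successes at every later visit; that depends on a coding choice they leave open. Nor do they support the same change in SAP 5.3.4, although its default is alike ("Else subject will be considered as a success of the endpoint for a given visit"). There the event is death from a catheter-related complication, and censoring at removal could discard a death from the very infection that led to the removal.

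**What to change.** 1. In the SAP 5.3.1 KM analysis, censor at the date of catheter removal for any reason, including infection and catheter dysfunction, when no CRBSI has occurred by then.
2. Still count a CRBSI that prompted the removal, and a device-related bloodstream infection attributed to the catheter soon after removal, within a window that the SAP states in advance.
3. Make the KM estimate the reported rate. Do not rely on the binary rate at 6 and 12 months, since counting these participants as successes and dropping them both bias it.
4. Reconcile Protocol 7.5, 7.2.1 and Appendix A on whether removal ends participation and is recorded as discontinuation. SAP 5.2.1 and 5.3.2 use the same removal list, so the answer should apply throughout.
5. Optionally add, as a sensitivity analysis, the cumulative incidence of CRBSI with removal as a competing event. It also helps if removal for a local infection is informative about CRBSI risk.
6. Leave SAP 5.3.4 able to count a catheter-related death after removal.

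The cost is SAP wording and a small programming change, using removal dates and reasons already on the re-interventions form. Fewer participants will be at risk at 6 and 12 months, so intervals will be slightly wider.
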